### 9.2.3 Expected SAEs

There are no expected SAEs previously documented for this intervention. Therefore, any that are assessed as having a causal relationship to the intervention will not undergo expectedness assessment and will be expedited to the REC as per section 9.2.4 below.

### 9.2.4 Reporting SAEs

The trial team will liaise with the treating physiotherapist/participant to compile all the necessary information. Once the SAE form has been completed, causality assessments will take place as per section 9.2.2 above. SAEs that are deemed possibly, probably or definitely related to the trial intervention by causality assessor will be notified to the REC within 15 days.

### 9.2.5 Follow-up of reported SAEs

Treating physiotherapists or the study team will monitor for changes to unresolved SAEs through ongoing monitoring during the intervention (treating physiotherapist) or via direct contact with the participant (study

team). If a treating physiotherapist becomes aware of any change of condition or other follow-up information, it should be reported to the study team by completion of another serious adverse event form (indicating that it is a follow-up report) as soon as it is available. Events will be followed up until the event has resolved or a final outcome has been reached where possible.

### 9.3 Responsibilities

*Table 4: SAE responsibilities*

Treating physiotherapists (responsible for delivery of the CMT intervention)	
Checking for AEs when participants attends for physiotherapy sessions
 
 
1. Ensuring that all SAEs are recorded and reported to the study team within 24 hours of becoming aware of the event and provide further follow-up information as soon as available. Ensuring that reported SAEs are chased with the study team if a record of receipt is not received within 2 working days of initial reporting.
 

Chief Investigator/delegate OR Independent clinical reviewer	
 
1. Clinical oversight of the safety of patients participating in the study, including an ongoing review of the risk / benefit
 
2. Using clinical judgement in assessing causality
 
3. Review of all related and unexpected SAEs
 

Trial team delegate (e.g. Trial manager/Statistician/Lead physiotherapist)	
 
1. Central data collection and verification of SAEs, according to the study protocol
 
2. Expectedness assessment of related SAEs
 
3. Reporting safety information to the CI, delegate, or independent clinical reviewer for the ongoing assessment of the risk / benefit.
 
4. Reporting safety information to the independent oversight committees identified for the study (Trial Steering Committee (TSC))
 

Sponsor delegate	
Review SAEs that are deemed possibly, probably or definitely related to the trial intervention.

Trial Steering Committee (TSC)	In accordance with the TSC charter, periodically reviewing safety data.
---------------------------------------	---

## 9.4 Notification of deaths

All deaths, when they are identified (up to the 12-month follow-up time-point), will be reported to the sponsor by the study team overseen by the CI, irrespective of whether the death is intervention-related, or an unrelated event. Deaths identified between six and 12 post-randomisation will be recorded for outcomes purposes but will not be classed as an SAE.

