#### 9.1.2 Serious Adverse Events (SAE)

An SAE is any untoward medical occurrence that fulfils one or more of the following criteria:

- Results in death
- Is immediately life-threatening
- Requires hospitalisation or prolongation of existing hospitalisation
- Results in persistent or significant disability or incapacity
- Is a congenital abnormality or birth defect
- Intervention is required to prevent one of the above or is an important medical condition

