## 9.2 Recording Adverse Events and Reporting Serious Adverse Events

### 9.2.1 Recording and reporting period

Intervention (CMT) group: All AEs and SAEs (unless otherwise specified) occurring from the time of informed consent until the six-month follow-up time-point must be recorded and reported as appropriate. Participants will be asked about anything that might constitute a SAE at the six-month follow-up questionnaire (see 'Adverse event question') and will also be given the opportunity to identify any events at every face-to-face physiotherapy session or via email/letter (sent to the trial team) during the intervention period.

Usual care group: The usual care group will be asked about anything that might constitute a SAE during the six-month follow-up questionnaire only questionnaire (see 'Adverse event question'). It will not be possible to collect a comparison dataset for the usual care group within this period without contaminating usual care. This is a pragmatic study, and the participants will not be contacted during the intervention period, unlike the intervention group. It is important not to contact the usual care group more than is necessary so as not to introduce bias. We anticipate a low risk of adverse events arising from usual NHS care.

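### Section 9.4 decides whether a death is an SAE by the date it is identified, contradicting the SAE definition in 9.1.2 and the occurrence-based window in 9.2.1

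*Protocol*

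**What the plan says.** Four parts of the protocol bear on how a death is classed.

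- Section 9.1.2 lists the criteria for an SAE. The first is "Results in death", with no condition on when the death becomes known.
- Section 9.2.1 sets the period for the CMT arm by occurrence: "All AEs and SAEs (unless otherwise specified) occurring from the time of informed consent until the six-month follow-up time-point must be recorded and reported". For the other arm it says: "The usual care group will be asked about anything that might constitute a SAE during the six-month follow-up questionnaire only".
- Section 9.4 opens with a reporting duty: "All deaths, when they are identified (up to the 12-month follow-up time-point), will be reported to the sponsor by the study team overseen by the" chief investigator, whether or not the death is related to the intervention. Its next sentence sets the classification: "Deaths identified between six and 12 post-randomisation will be recorded for outcomes purposes but will not be classed as an SAE". The unit after the two numbers is missing; months are evidently meant.
- Section 9.2.4 states what follows from SAE status: "SAEs that are deemed possibly, probably or definitely related to the trial intervention by causality assessor will be notified to the REC within 15 days". The causality grading in section 9.2.2 (Table 3) is likewise written for SAEs.

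All-cause mortality and serious adverse events are separate secondary outcomes in section 3.3. Table 2 collects deaths during the intervention period and at 6 and 12 months.

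**The concern.** The date on which the team learns of a death and the date on which it happened are different things, and 9.4 uses the first where 9.2.1 uses the second. A death inside the safety window but discovered after it is then classed one way by 9.1.2 and 9.2.1 and the opposite way by 9.4. Staff completing the forms have no clear rule.

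If 9.4 is followed, the death gets no SAE form and no causality grading. If it was possibly related to CMT, the 15-day notification to the ethics committee is not triggered. The count of SAEs, itself a listed outcome, would also omit a fatal event from the period it is meant to cover.

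**Working it through.** The protocol gives no death rate and no expected number of SAEs, so there is no figure to reproduce. The check compares the rules and then the timeline.

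**Step 1: one death under each rule.** Take a CMT participant who dies in month 3 and whose death is discovered in month 7.

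- 9.1.2: the event resulted in death, so it is an SAE.
- 9.2.1: it occurred between consent and six months, so it must be recorded and reported.
- 9.4: it was identified between six and 12 months, so it is not classed as an SAE.

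For a usual-care participant the conflict with 9.1.2 is the same. Section 9.2.1 states the occurrence window expressly only for the CMT arm.

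**Step 2: is *identified* a slip for *occurring*?** The preceding sentence in 9.4 uses the word to mean discovered, since deaths are reported when they are identified. The second sentence naturally carries the same meaning. Section 9.2.1 also allows for exceptions (unless otherwise specified), so a reader could take 9.4 as the specific rule that overrides it.

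**Step 3: compare a non-fatal SAE.** Under 9.2.2, if a follow-up questionnaire points to a possible SAE, the participant is contacted and an SAE form completed if applicable. A month-3 hospital admission learned of through the six-month questionnaire is therefore handled as an SAE. A month-3 death learned of a week later, during the reminders, is not, if 9.4 is followed.

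**Step 4: can deaths inside the window plausibly be found late?**

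- Usual care: for safety purposes "the participants will not be contacted during the intervention period, unlike the intervention group". The only planned SAE enquiry is the six-month questionnaire, which a participant who has died cannot return.
- CMT: section 8.7 aims for a start within 7 weeks of randomisation and delivery over 7 to 9 weeks. A start at week 7 gives a last session at 7 + 7 = 14 to 7 + 9 = 16 weeks, consistent with the stated four months. Enquiry at sessions then stops before month 6, although completion is allowed up to six months.
- Both arms: the section 8.8 reminders run at 3 days, 1 week, 2 weeks (with a call) and 3 weeks (by telephone) after the six-month invitation. These are the contacts most likely to reveal a death, and they fall after six months.

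**Step 5: scale, under an assumption.** The protocol plans 126 participants per arm. Assume annual mortality of 0.5% to 2%; this range is not from the protocol.

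- Deaths per arm in months 0 to 6: 126 × 0.5 × 0.005 = 0.3 to 126 × 0.5 × 0.02 = 1.3.
- CMT deaths in months 4 to 6: 126 × (2/12) × 0.005 = 0.1 to 126 × (2/12) × 0.02 = 0.4.

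These are expected deaths in those periods, not expected misclassifications. Only those discovered after six months would be affected.

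**The case against.** The strongest reply is that 9.4 is loose wording for deaths that happen in months 6 to 12. The sentence even omits its unit, and 9.2.1 and 9.2.2 apply no identification cut-off to other SAEs. That may be what was intended. It supports correcting the sentence, because the wording as it stands says something else. It also means that for CMT this is a contradiction between sections, and a reader should not infer that CMT deaths after the last session are definitively excluded.

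Three further inferences are tempting and go beyond the protocol.

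- *Nearly all early usual-care deaths would be missed, or a fixed share of the CMT window is uncovered.* Neither can be derived. The protocol does not say how deaths are identified. A relative answering a letter or newsletter, the GP (informed of participation with permission) or site staff may report sooner. CMT start and finish dates vary, so the period without sessions may be longer or close to nothing.
- *These deaths escape safety oversight.* They do not. Every death identified up to 12 months goes to the sponsor and counts in all-cause mortality. In usual care, relatedness to CMT would hardly arise, so little is lost there beyond the SAE count.
- *Section 9.4 makes CMT look worse on SAEs.* Most of the unequal ascertainment comes from 9.2.1, which discloses and defends it as avoiding extra contact with usual care. Correcting 9.4 leaves that untouched for non-fatal SAEs. However, the defence does not extend to declassifying a death already known to have occurred inside the window, since using its date needs no contact.

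**Conclusion.** The contradiction is in the text and should be corrected. Followed literally, 9.4 removes SAE status from a death that occurred before six months but was discovered afterwards. What is lost is the SAE label, the SAE form, the causality assessment and, for a death possibly related to CMT, the 15-day notification. In usual care the consequence is mainly an undercount of SAEs.

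The number affected is probably very small and cannot be derived from the protocol. At the assumed mortality of 0.5% to 2% per year, about one death or fewer per arm would be expected in the whole six months, and only late-discovered deaths matter. The case for correction rests on the severity of each event and the low cost of the change. All-cause mortality and the primary outcome are unaffected.

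**What to change.** Reconcile 9.1.2, 9.2.1 and 9.4 by keying the second sentence of 9.4 to the date of death, for both arms. For example: *Deaths occurring up to six months post-randomisation are SAEs whenever they are identified; deaths occurring after six months and up to 12 months are recorded for outcome purposes.* This also supplies the missing unit. Record both the date of death and the date of identification, so that the classification can be audited.

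The cost is one sentence in the protocol, handled through the amendment process, and one added date field on the form. No further participant contact is needed.

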## 9.5 Reporting urgent safety measures

If any urgent safety measures are taken the CI/Sponsor shall immediately and in any event no later than three days from the date the measures are taken, give written notice to the relevant REC of the measures taken and the circumstances giving rise to those measures.

# 10 STATISTICS AND DATA ANALYSIS

## 10.1 Sample size calculation and attrition

The minimally clinically importance difference in the primary outcome, the composite WOMAC score is 17-22% [38]. This trial is therefore powered to detect a 20% difference between groups in the composite WOMAC score at the primary end point (12 months). In our feasibility study, the baseline mean (SD) of the composite WOMAC score was 41.3 (17.8). A 20% change therefore equates to a change of 8.3 points, which gives an effect size of 0.46. Based on these estimates, 101 participants per group obtains 90% power for a two-sided test with type 1 error ( $\alpha$ ) set at 5%. Accounting for 20% attrition indicates a target of 126 participants per group.

We have mapped specific initiatives to reduce attrition. These include financial incentives, regular communication to participants through a newsletter and creation of a dedicated outcome data collection reminder schedule. With these additional measures, we are confident we can achieve an attrition rate less than 20%.

## 10.2 Planned recruitment rate

In our previous feasibility study, we tested the potential to recruit participants using the same inclusion/exclusion criteria as this study. Working with three MSK CATs departments (not physiotherapy departments or GPs), we

were able to randomise a total of 82 participants over a 10-month period. This equates to a recruitment rate of 2.7 per site per month. We have assumed the slightly lower rate of recruitment of 2.33 participants per site per month for this trial. With an 18-month recruitment period, this equates to 252 participants (6 sites x 18 months x 2.33).

### 10.3 Summary of baseline data and flow of participants

Analyses will be reported in line with the CONSORT statement. Descriptive statistics will be presented to summarise the distribution of baseline variables across each of the two randomisation groups. The continuous baseline variables (age, height, weight, duration of knee pain symptoms) will be reported with means & standard deviations, if shown to be normally distributed, using a combined skewness and kurtosis test, otherwise will be reported with medians and interquartile ranges (IQR).

A Consolidated Standards of Reporting Trials (CONSORT) flow diagram will be produced, showing the frequency of participants:

- Screened for eligibility
- Reason for not being eligible,
- Found eligible,
- Reasons not approached,
- Approached
- Excluded before consent and reason for exclusion
- Consented
- Excluded before randomisation and reason for exclusion,
- Randomised
- Allocated to each randomisation group
- That received each allocated intervention
- That did not receive each allocated intervention
- Lost to follow-up (and the frequency of each reason for loss to follow-up) for each analysis group,
- Analysed for each analysis group,
- Not analysed (and the frequency of each reason for not being analysed) for each analysis group.

### 10.4 Primary outcome analysis

*Population:* All participants

*Treatments:* CMT + Usual care vs usual care alone , regardless of non-adherence or receipt of surgery to treat knee OA.

*Primary outcome:* Mean difference in WOMAC composite score at 12-month follow-up

*Handling of intercurrent events*

- Failure to complete CMT (attending fewer than 6 out of 7 sessions) – Treatment policy strategy
- Surgery to treat knee OA – Treatment policy strategy

The primary analysis will adopt a treatment policy strategy in line with the ICH E9(R1) estimand framework. All intercurrent events occurring after randomisation, including failure to complete the CMT intervention

(attending fewer than 6 out of 7 sessions) or undergoing knee surgery, will be considered part of the treatment effect. Participants will be analysed in the arm to which they were randomised regardless of these events. The primary outcome will be the adjusted mean difference in WOMAC composite score at 12 months: this will be estimated using a linear multilevel analysis of covariance (ANCOVA) model, including treatment arm (fixed effect), baseline WOMAC as a covariate, and site and receipt of surgery as random effects. The estimate of the difference for the WOMAC composite score between intervention arms will be presented with 95% confidence intervals and p-values: statistical tests will be two-sided. Missing primary outcome data will be replaced using multiple imputation under missing-at-random assumptions, and analyses will be conducted using the Stata MI command.

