## 5 TRIAL SETTING

This is a multi-centre randomised controlled trial, taking place in physiotherapy services based in NHS hospitals across the UK. We expect to open six sites, with scope of increasing this number if required. To ensure inclusivity we will work with a range of NHS hospitals serving diverse communities in rural and urban communities. At each site there will be two physiotherapists who will be trained to deliver the CMT intervention. Participants in the CMT arm of the trial will receive the CMT intervention at one of these research sites.

All sites are expected to be recruiting sites, undertaking all research activities. At each site, the CMT intervention will be delivered within a dedicated physiotherapy clinical space. However, in the case that a particular trust is unable to provide space for intervention delivery, a GP practice or community space (such as a private room in a community centre) within close proximity of the research site, will be used to deliver the

CMT intervention. The intervention may also be delivered within a dedicated clinical space at the University of Salford which is close to one of the research sites.

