After a period of 1-3 months (depending on physiotherapist preference and timing of recruitment for the main clinical trial), physiotherapists will be invited back for a third (final) face-to-face workshop. At this workshop, the research team will go through any aspects of the CMT protocols which the physiotherapists have found particularly challenging to understand/deliver and then carry out a final competency check. For this final check, physiotherapists will be expected to have in-depth knowledge of the protocols and have memorised every stage.

Experience from previous trials shows that physiotherapists require exposure to a range of different presentations of knee OA before they can be fully confident in adapting and applying the CMT protocols for different patients. Therefore, we propose to provide direct supervision for each physiotherapist when they treat the first 3-4 participants. This supervision will be provided by a member of the research team either through direct observation or through video recording and subsequent follow-up. We recognised that some participants may not feel comfortable with being videoed and therefore we will make this optional. All recordings will be stored securely on a University of Salford server and deleted once analysis has been completed, typically within 2-3 weeks of the recording.

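### The primary model and sample size make no allowance for clustering by CMT physiotherapist, so the primary test is anti-conservative if the therapist ICC is above zero

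*Protocol*

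**What the plan says.** Protocol section 5: "At each site there will be two physiotherapists who will be trained to deliver the CMT intervention". Section 6.3 expects at least six sites, hence at least 12 physiotherapists, and requires that they take no part in the care of controls. Section 6.2 describes seven individual sessions of about an hour, with hands-on guidance and tailoring to the participant.

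Section 10.4 writes the primary model out: "this will be estimated using a linear multilevel analysis of covariance (ANCOVA) model, including treatment arm (fixed effect", followed by baseline WOMAC as a covariate and random effects for site and for receipt of surgery. Section 10.5 applies consistent methods to the secondary outcomes. Section 10.6 plans per-protocol and complete-case analyses only.

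Section 10.1 states that "the baseline mean (SD) of the composite WOMAC score was 41.3 (17.8"), that "A 20% change therefore equates to a change of 8.3 points, which gives an effect size of 0.46", and that "Based on these estimates, 101 participants per group obtains 90% power for a two-sided test". It then says: "Accounting for 20% attrition indicates a target of 126 participants per group". It mentions neither an ICC nor a design effect.

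**The concern.** Physiotherapists are nested in one arm. If some obtain better results than others, CMT participants who share a physiotherapist have correlated outcomes, while controls have no trial physiotherapist and no such correlation. This partially nested structure adds a variance component to the CMT mean.

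The site random intercept does not capture it. That intercept is common to both arms, so it cancels from the within-site treatment contrast. The difference between the two physiotherapists at a site exists in the CMT arm alone and stays in the treatment estimate.

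At stake are the width of the primary confidence interval and the validity of its p-value, the same for the secondary outcomes, and the meaning of the 90% power statement.

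**Working it through.** **Inputs from the protocol.** Alpha 0.05 two-sided, 90% power, effect size d = 0.46, SD 17.8, 101 analysed and 126 randomised per arm (10.1); 12 physiotherapists (6.3).

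**Assumptions.** Therapist ICC 0.01 to 0.10, on the total variance; baseline to 12-month correlation r of 0 or 0.5; equal caseloads. The protocol gives none of these.

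**Step 1: the protocol's own figure.** An independent two-sample t-test at d = 0.46 needs 101 per arm (power 90.2%). Then 101/0.8 = 126.25, stated as 126. The figure therefore reproduces with a design effect of 1, that is, with no clustering allowance.

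**Step 2: add the therapist component.**
- Analysed participants per physiotherapist: m = 101/12 = 8.42.
- Design effect in the CMT arm: DE = 1 + (m - 1) x ICC. At 0.05 this is 1 + 7.42 x 0.05 = 1.371.
- Variance of the standardised difference, ignoring therapist: V0 = 2(1 - r²)/101.
- Variance with therapist: V = V0 + ICC x (m - 1)/101.
- Ratio of true to reported standard error: k = sqrt(V/V0).
- Type I error if ignored: 2 x [1 - Φ(1.96/k)].
- Power with the correct standard error: Φ(0.46/sqrt(V) - 1.96).

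These are normal approximations, so unadjusted power at ICC 0 comes out at 90.5% and not 90.2%.

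| ICC | DE | k, r=0 | Type I, r=0 | Power, r=0 | k, r=0.5 | Type I, r=0.5 | Power, r=0.5 |
|---|---|---|---|---|---|---|---|
| 0 | 1.000 | 1.000 | 5.0% | 90.5% | 1.000 | 5.0% | 96.5% |
| 0.01 | 1.074 | 1.018 | 5.4% | 89.4% | 1.024 | 5.6% | 95.8% |
| 0.03 | 1.222 | 1.054 | 6.3% | 87.3% | 1.072 | 6.7% | 94.1% |
| 0.05 | 1.371 | 1.089 | 7.2% | 85.1% | 1.117 | 7.9% | 92.2% |
| 0.10 | 1.742 | 1.171 | 9.4% | 79.7% | 1.222 | 10.9% | 87.0% |

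In WOMAC points, at r = 0.5 and ICC 0.05, the reported standard error is 17.8 x sqrt(1.5/101) = 2.17. The true one is 17.8 x sqrt((1.5 + 0.371)/101) = 2.42. The 95% interval would be reported as about ±4.25 when it should be about ±4.75.

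**Step 3: simulation.** Trials were simulated with 6 sites, 12 physiotherapists, about 101 per arm and a site-adjusted ANCOVA without a therapist term (1,500 to 8,000 trials per setting where the count is on record). Type I error was 4.7-5.5% at ICC 0, 4.9-5.8% at 0.01, 6.1-6.7% at 0.03, 7.6-8.7% at 0.05 and 9.4-10.8% at 0.10. This agrees with the formula and confirms that adjusting for site does not remove the problem.

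**The case against.** The strongest reply is that the ICC may be close to zero by design. Section 6.2 describes a clearly delineated treatment protocol. Section 6.4 sets 15 online modules, three workshops, two competency assessments and supervision of each physiotherapist's first 3-4 participants. Section 6.6 scores fidelity from 14 recordings per physiotherapist. Section 6.4 does say that "physiotherapists require exposure to a range of different presentations of knee OA before they can be fully confident", but it says so to justify that supervision. This stands as far as it goes: these measures may keep the ICC low, and at 0.01 the effect is negligible. They do not make it zero, which is what the model assumes. Twelve physiotherapists is also a minimum; more would mean smaller caseloads and less inflation.

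Three stronger readings are tempting, and the protocol does not support them.
- *The error favours CMT.* The test is two-sided and the inflation is symmetric: a false finding of harm becomes more likely by the same amount.
- *The trial is too small.* Section 10.1 takes no credit for baseline adjustment. At r = 0.5 that adjustment more than offsets the loss at ICC 0.05 and leaves 87% at 0.10.
- *No more participants could be needed.* That is not secure either. It rests on an assumed correlation, and an approximate small-sample df correction lowers the adjusted power to about 91% (ICC 0.05) or 85% (ICC 0.10).

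An analysis plan not shown here could add a therapist term. However, section 10.4 lists the model terms explicitly, so the two documents would then disagree.

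**Conclusion.** The omission is real. The protocol creates clustering by physiotherapist in one arm, writes out a primary model that ignores it, and sizes the trial without it. The consequence is conditional: the standard error is too small only if the therapist ICC is above zero, and the protocol gives no value. Over an assumed range, two-sided type I error is about 5-6% at 0.01, 6-7% at 0.03, 7.5-9% at 0.05 and 9-11% at 0.10. These figures rest on 12 physiotherapists with equal caseloads and 101 analysed per arm.

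Power at 101 per arm is about 89%, 85% or 80% unadjusted at ICC 0.01, 0.05 or 0.10. With an assumed baseline correlation of 0.5 it is about 96%, 92% or 87% before any df correction. The point therefore rests on the validity of the interval and p-value, not on recruitment. It should be corrected, because the correction is cheap and the ICC cannot be assumed to be nil.

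**What to change.** **Section 10.4.** Add a therapist random effect in the CMT arm only: a partially nested model with arm-specific residual variances, fitted by REML with a small-sample df correction for about 12 clusters. Treat controls and never-treated CMT participants as singletons. Carry this through to the secondary outcomes under 10.5. The receipt-of-surgery term is a separate matter and is not altered by this change.

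**Sections 6.5, 8.7 and 11.1.** Add the treating physiotherapist's identifier to the data transferred to the trial database. Section 6.5 lists only session dates and attendance for transfer, and 11.1 restricts access to the treatment logs to the lead or fidelity-monitoring physiotherapist and the treating physiotherapists. Section 8.7 limits the treatment-log data used in the final analysis to attendance, so it must be amended to allow the identifier.

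**Section 10.1.** State power over an assumed ICC range, such as 0.01 to 0.10, together with the baseline correlation assumed.

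**Cost.** One extra data item, best captured before data accrue, and edits to these sections; no extra visits or staff. The interval will be slightly wider if the ICC is positive, and a therapist variance estimated from about 12 clusters will be imprecise. If the sponsor keeps the present primary model, a prespecified sensitivity analysis with the therapist effect is the minimum.
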